4.2.2 Subject Evaluation & Statistics

The Per-Protocol (PP) Population for DLT Assessment includes:

- All subjects who experience a DLT at any time during the DLT Evaluation Period (as defined in Section 3.1.9)
- All subjects with no DLT who receive at least 75% of the scheduled doses of MEDI4736, motolimod (pre Amendment 2), and PLD as well as respective safety assessments, without major protocol violations, over the entire DLT Evaluation Period (as defined in Section 3.1.9).

Refer to Section 3.1.11 for subject replacements.

The Intent-To-Treat (ITT) Population for safety and tolerability is defined as all subjects who receive at least one dose of PLD, motolimod (pre Amendment 2) or MEDI4736.

In Phase 1, for the primary endpoint of determining DLTs and the MTD, the analysis of safety and tolerability will be based on the PP Population for DLT Assessment.

In both Phases 1 and 2, the overall analysis of safety and tolerability will be based on the ITT Population for safety and tolerability.

Appropriate summaries of AEs, laboratory data and vital sign data will be presented. Adverse events will be coded using the MedDRA dictionary. Incidences of treatment-emergent adverse events (TEAE, those events that started after dosing or worsened in severity after dosing) will be presented overall and by maximum severity (according to CTCAE version 4.03) and relationship to study medication.

For each continuous laboratory parameter, results will be categorized as low, normal, or high based on the laboratory normal ranges. Frequencies and percentages will be presented by treatment arm for the shifts in these categories (i.e., low to normal, low to high, high to low, etc.) from baseline to each post-treatment assessment time point. Additionally, for each continuous hematology and chemistry parameter, descriptive statistics will be presented by treatment arm for the changes from baseline to each post-treatment assessment time point. Descriptive statistics will be presented by cohort for the changes in vital signs from baseline to each post-treatment assessment time point.

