6.3.4 MEDI4736 Administration

Following preparation of the dose, MEDI4736 will be administered according to the following guidelines:

- The entire contents of the IV bag should be administered as an IV infusion over approximately 60 (\pm 5) minutes, using a 0.2- or 0.22- μ m in-line filter. **An infusion of less than 55 minutes is considered a deviation.**
- After the contents of the IV bag are fully administered, the IV line will be flushed with a volume of IV diluent equal to the priming volume of the infusion set used. Alternatively, the infusion will be completed according to institutional policy to ensure the full dose is administered; documentation is required if the line was not flushed.
- MEDI4736 must be administered at room temperature by controlled infusion into a peripheral vein or central line. Prior to the start of the infusion, ensure that the bag contents are at room temperature to avoid an infusion reaction due to the administration of the solution at low temperatures.
- MEDI4736 solution should not be infused with other solutions or medications.
- A physician must be present at the site or immediately available to respond to emergencies during all administrations of investigational products. Fully functional resuscitation facilities should be available.
- MEDI4736 must not be administered via IV push or bolus but as an IV infusion.
- The date, start time, interruption, and completion time of MEDI4736 administration must be recorded in the source documents.
- Subjects will be monitored before, during and after infusion with assessment of vital signs according to Section 6.3.5.
- See Section 8.4.2.2 for management guidelines for infusion-related reactions.
- The total time between needle puncture of the MEDI4736 vial to start of administration should not exceed 4 hours at room temperature, or 24 hours at 2°C to 8°C (36°F to 46°F). Standard infusion time is 60 \pm 5 minutes. However, if there are interruptions during infusion, the total allowed infusion time should not exceed 8 hours. In the event that either preparation time or infusion time exceeds the time limits, a new dose must be prepared from new vials.

MEDI4736 does not contain preservatives, and any unused portion must be discarded.

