8.4.2.2 Infusion-related Reactions

Grade 1	
 • The infusion rate of MEDI4736 may be decreased 50% or temporarily interrupted until resolution of the event. • Acetaminophen and/or antihistamines may be administered per institutional standards at the discretion of the Investigator. • Premedication for subsequent doses should be considered. • Steroids should not be used for routine premedication of \leqGrade 2 infusion reactions
Grade 2	
 • Same as Grade 1, but consider giving subsequent infusions at 50% of the initial infusion rate.
Grade 3-4	
 • The infusion must be stopped immediately and treatment permanently discontinued. • Manage severe infusion-related reactions per institutional standards (e.g., IM epinephrine, followed by IV diphenhydramine and ranitidine, and IV glucocorticoid).

CONFIDENTIAL

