### **3.9.3 Vital Signs**

For vital signs, descriptive statistics will be presented for changes from pre-dose to end of infusion on MEDI4736 dosing days in the first two cycles and for On Study Follow-up assessments. End of infusion time points and change from pre-dose to end of infusion for subjects who experienced an interruption in the study drug administration (administration was stopped and subsequently restarted) will not be included.

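### The only vital-sign summary table drops infusions that were stopped and restarted, and stopping is one of two permitted responses to a Grade 1–2 infusion reaction

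*SAP*

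**What the plan says.** SAP 3.9.3 limits the vital-sign summary to "changes from pre-dose to end of infusion on MEDI4736 dosing days in the first two cycles and for On Study Follow-up assessments". It then sets an exclusion: "End of infusion time points and change from pre-dose to end of infusion for subjects who experienced an interruption in the study drug administration". The bracket that follows defines an interruption and completes the rule: "administration was stopped and subsequently restarted) will not be included". No reason is given. The result is Table 14.4.5 (ITT population), the only vital-sign table in the SAP's list of tables. SAP 3.1.2 has summaries presented by cohort, with minimum and maximum among the statistics.

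Protocol 4.2.2 plans something wider and without an exclusion: "Descriptive statistics will be presented by cohort for the changes in vital signs from baseline to each post-treatment assessment time point".

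Protocol 8.4.2.2 sets out how infusion reactions are handled. For Grade 1: "The infusion rate of MEDI4736 may be decreased 50% or temporarily interrupted until resolution of the event". For Grade 2: "Same as Grade 1, but consider giving subsequent infusions at 50% of the initial infusion rate". For Grade 3–4: "The infusion must be stopped immediately and treatment permanently discontinued". Protocol 6.3.4 also provides for interruptions without linking them to a reaction: "However, if there are interruptions during infusion, the total allowed infusion time should not exceed 8 hours".

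**The concern.** A summary of vital-sign change across an infusion is there to show what the infusion does to blood pressure, heart rate and the other signs. If a record can be removed because the subject reacted during that infusion, the exclusion depends in part on the outcome being summarised. The likely direction is towards a more benign table, and the extremes would suffer most, since one reacting subject can supply the minimum or maximum.

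This matters because hypersensitivity and infusion reactions are adverse events of special interest (Protocol 7.1.8), with hypotension and hypertension among their listed features. Adverse event tables count and grade reactions but do not summarise the size of the vital-sign change. The rule also sits oddly beside SAP 3.1.5, which takes the worst result when repeated pre-dose assessments at one time point include an abnormal one.

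**Working it through.** The plan states no figure to reproduce: it gives no infusion-reaction rate, interruption rate or vital-sign standard deviation. The check is a comparison of texts, followed by an illustration on assumed values.

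**Step 1: which infusions the rule removes.** SAP 3.9.3 set against Protocol 8.4.2.2 and 6.3.4:

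| Situation | Stopped and restarted? | In Table 14.4.5? |
|---|---|---|
| Grade 1–2 reaction, rate halved | No | Yes |
| Grade 1–2 reaction, temporarily interrupted | Yes | No |
| Grade 3–4 reaction, permanently stopped | No | Not removed by the rule |
| Interruption for another cause | Yes | No |

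Only the second row is exclusion because of a reaction. The fourth is exclusion unrelated to outcome. The SAP does not ask for a count of either.

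**Step 2: per infusion or per subject.** The rule is worded in terms of subjects, so it can mean the interrupted infusion alone or all of that subject's end-of-infusion records. On the Q4W schedule, cycles 1–2 hold 2 MEDI4736 infusions per subject. For 41 subjects (the Phase 2 evaluable target, used here only as a round denominator) that is 2 × 41 = 82 planned infusions. If 1 to 6 subjects have one interrupted infusion each, the rule removes 1 to 6 records per infusion, or 2 to 12 per subject. At dose level 0a (Q2W) there are 4 infusions in two cycles, so the same ambiguity is 1 record against 4.

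**Step 3: possible size, on assumptions.** Take n = 41 and one infusion visit. Let k subjects be interrupted with mean change d at end of infusion; the rest have mean change 0; the SD within each group is 8 mmHg. With the exclusion the table shows mean 0, SD 8. With everyone included:

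- mean = k·d/n
- SD = √(8² + (k/n)(1 − k/n)d²)

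| k (share of 41) | d (mmHg) | Mean | SD |
|---|---|---|---|
| 1 (2.4%) | -10 | -0.24 | 8.1 |
| 4 (9.8%) | -20 | -1.95 | 10.0 |
| 6 (14.6%) | -30 | -4.39 | 13.3 |

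If the value has recovered by the end of the infusion, d = 0 and including the record leaves the mean unchanged. In a cohort of 6, one interrupted subject is a sixth of the data: d of -10 to -30 gives -10/6 = -1.7 to -30/6 = -5.0 mmHg.

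**Step 4: what readings exist.** For the first four MEDI4736 doses, Protocol 6.3.5 takes vital signs before dosing, every 15 minutes during infusion, at the end, and 30 and 60 minutes after. Cycles 1–2 contain 2 infusions (Q4W) or 4 (level 0a), so every infusion in the summary falls under that fuller schedule. The readings during and after infusion are not summarised for anyone.

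**The case against.** A reader might infer that Table 14.4.5 omits exactly the infusions in which vital signs changed. The documents do not support that. Interruption is optional for Grade 1–2 and slowing the rate is the alternative. The most severe reactions are not restarted and so do not meet the SAP's definition. Interruptions can have other causes. No vital-sign data are given to show where the changes lie. All of this stands.

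A second objection is that the pause lasts until the reaction has resolved, so the end-of-infusion reading may be a recovered one. It may also follow acetaminophen or antihistamines, and the infusion may run up to 8 hours in total against a standard 60 ± 5 minutes. Pooling such readings with standard ones raises a comparability problem, which could be the unstated reason for the rule. This also stands. It means that restoring the end-of-infusion value alone would not be a full remedy. It does not justify dropping the records without a count.

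Third, the data are not lost. SAP 3.9 puts all subject data in listings. Listing 16.2.25 covers vital signs, and Listing 16.2.18 covers adverse events leading to drug interruption or discontinuation. Clinically significant abnormalities are recorded and graded as adverse events. The table is descriptive and nothing is tested on it. These points limit the consequence, but none supplies a summary of how large the changes were.

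**Conclusion.** The point holds in a limited form. The exclusion is partly outcome-dependent, departs from Protocol 4.2.2, is unexplained, and is ambiguous between infusion and subject. It reaches Grade 1–2 reactions managed by stopping and restarting, together with interruptions from any other cause.

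The size of any bias is unknown. The range of 0.24 to 4.39 mmHg in the mean rests entirely on the assumed interruption counts, the assumed changes of -10 to -30 mmHg, all changes being falls, and no recovery by the end of the infusion. With recovery it could be close to zero; in a small cohort one subject could matter more. A bias towards no effect is plausible, not demonstrated. The primary endpoint and the DLT criteria are untouched. This is a worthwhile and inexpensive improvement to a safety summary, not a flaw that threatens the trial's conclusions.

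**What to change.** Amend SAP 3.9.3 and the shell of Table 14.4.5 as follows:

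1. Keep all MEDI4736 infusions of cycles 1–2 in the vital-sign summary. Show interrupted and permanently stopped infusions in a separate row, with the number of each and the reasons. This avoids mixing end-of-infusion readings taken at very different times.
2. Add the worst change from pre-dose during or after infusion, in each direction, from the readings already collected under Protocol 6.3.5. An interrupted infusion may yield more readings, and a worst value over more readings is more extreme by chance. That is another reason for the separate row.
3. If any exclusion is kept for a secondary view, apply it per infusion and not per subject, give the reason, and note the departure from Protocol 4.2.2.

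The cost is one derived variable, a few extra table rows and SAP wording. No new data and no change to how reactions are managed are needed.

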### **3.9.4 ECOG Performance Status**

ECOG Performance Status will be summarized by cohort by presenting the number and percentage of subjects with ECOG score 0, 1, 2, 3, and 4 at baseline and ECOG score of 0, 1, 2, 3, 4, and 5 at the last on-treatment assessment time point (including optional treatment extension time points) and last on-study follow-up time point for which ECOG Performance Status was assessed. ECOG data will be provided in a subject listing.

### **3.9.5 12-Lead ECG**

Shift of normality status (normal, abnormal with no clinical significance, abnormal with clinical significance) from baseline to each selected post-treatment assessment time point will be presented for the ECG data. Based on the number of subjects who had non-missing results for both baseline and corresponding post-treatment assessment time point, percentages for the shift tables will be calculated. ECG results will be provided in a subject listing.

### **3.9.6 ECHO or MUGA**

For the ECHO or MUGA data, shift of normality status (normal, abnormal with no clinical significance, abnormal with clinical significance) from baseline to each selected post-treatment assessment time point will be presented. Percentages for the

shift tables will be calculated based on the number of subjects who had non-missing results for both baseline and corresponding post-treatment assessment time point. ECHO and MUGA data will be provided in a subject listing.

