#### **3.1.2 Reporting of Numerical Values**

All clinical study data will be presented in subject data listings. All by-visit summarizations will be conducted using data from Cycle 1, Cycle 2, and/or the last cycle, as applicable. All data presentations will be by the planned cohorts in the protocol, separately for Phase 1 and Phase 2.

Descriptive statistics (n, mean, standard deviation, median, minimum and maximum) will be calculated by cohort for continuous variables.

Frequencies and percentages will be presented by cohort for categorical and ordinal variables. If there are missing values, the number missing will be presented, but without a percentage.

Means and medians will be reported to one decimal place more than the data reported in the EDC. Standard deviations will be reported to two decimal places more than the data reported. Minimum and maximum will be reported to the same number of decimal places captured in the EDC.

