### 3.3.2 Safety Variables

Safety variables include:

- Incidence of treatment emergent adverse events (TEAEs), defined as an adverse event (AE) that is first identified, or is identified to worsen in intensity, at a time point occurring after the first dose of study drug
  - All TEAEs by System Organ Class (SOC) and Preferred Term (PT)
  - All TEAEs by PT
  - TEAEs by maximum severity (according to CTCAE version 4.03)
  - Treatment related TEAEs (TRAЕ) defined as events with a relationship to any study drug of ‘Definitely Related’, ‘Probably Related’ or ‘Possibly Related’
  - Treatment related TEAEs by maximum severity (according to CTCAE version 4.03)
  - TEAEs leading to study drug withdrawal
  - Serious TEAEs
- Change in clinical laboratory parameters (hematology, chemistry, amylase, lipase, thyroid) from baseline to each selected post-treatment assessment time point and shifts in clinical laboratory parameters from baseline to each selected post-treatment assessment time point
- Change in vital signs (systolic and diastolic blood pressure, heart rate, respiratory rate, and body temperature) from pre-dose to end of infusion at selected post-treatment assessment time points
- Change in ECOG performance status from baseline to last assessment
- Shifts in ECG from baseline to each selected post-treatment assessment time point

- Shifts in ECHO or MUGA from baseline to each selected post-treatment assessment time point

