## **3.9 Safety Analysis**

All safety analyses will be performed using the ITT population. For clinical laboratory, data collected from all core study cycles and/or on-study follow-up assessments will be analyzed for each subject. For vital signs, ECOG performance status, and ECG, only data collected from the first two cycles and/or on-study follow-up assessments will be analyzed for each subject. All subject data including those from the additional cycles will be presented in subject listings.

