### **3.9.2 Clinical Laboratory Evaluation**

For each continuous laboratory (hematology and chemistry) parameter, results will be categorized as low, normal, or high based on the laboratory normal ranges.

Frequencies and percentages will be presented by cohort and overall for the shifts in these categories from baseline to selected post-treatment assessment time points (i.e., low to normal, low to high, high to low, etc.). Percentages for the shift tables will be calculated based on the number of subjects who had results for both baseline and the corresponding post-treatment assessment time point. Additionally, for continuous hematology and chemistry parameters, descriptive statistics will be presented for the changes from baseline to each selected post-treatment assessment time point.

Abnormal laboratory values with their clinical significance status will be presented in a subject listing.

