Table 14.3.6.4	Incidence of Pegylated Liposomal Doxorubicin (PLD) Related Adverse Events By Maximum CTCAE Grade, MedDRA System Organ Class and Preferred Term, ITT Population
Table 14.3.7.1	Incidence of Treatment Related Adverse Events Leading to MEDI4736 Withdrawal by MedDRA System Organ Class and Preferred Term, ITT Population
Table 14.3.7.2	Incidence of Treatment Related Adverse Events Leading to Motolimod Withdrawal by MedDRA System Organ Class and Preferred Term, ITT Population
Table 14.3.7.3	Incidence of Treatment Related Adverse Events Leading to PLD Withdrawal by MedDRA System Organ Class and Preferred Term, ITT Population
Table 14.3.8	Incidence of Serious Adverse Events by MedDRA System Organ Class and Preferred Term, ITT Population
Table 14.4.1	Hematology Parameters – Change from Baseline, ITT Population
Table 14.4.2	Hematology Parameters – Shift from Baseline, ITT Population
Table 14.4.3	Chemistry Parameters – Change from Baseline, ITT Population
Table 14.4.4	Chemistry Parameters – Shift from Baseline, ITT Population
Table 14.4.5	Vital Signs – Change from Pre-dose to End of Infusion, ITT Population

Table 14.4.6	ECOG Performance Status at Baseline and Last Assessment, ITT Population
Table 14.4.7	ECG-Shift from Baseline, ITT Population
Table 14.4.8	ECHO or MUGA-Shift from Baseline, ITT Population

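### ECHO/MUGA is summarised only as a normality shift at undefined time points; read literally, the SAP's by-visit rule would leave most on-treatment scans out of the table

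*SAP*

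**What the plan says.** SAP 3.9.6 opens: "For the ECHO or MUGA data, shift of normality status (normal, abnormal with no clinical significance, abnormal with clinical significance) from baseline". It promises this for each selected post-treatment time point without listing the points. The safety variable in SAP 3.3.2 has the same form: "Shifts in ECHO or MUGA from baseline to each selected post-treatment assessment time point". The only table is 14.4.8, titled "ECHO or MUGA-Shift from Baseline, ITT Population". Beyond that, "ECHO and MUGA data will be provided in a subject listing" (Listing 16.2.28).

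Two general provisions bear on which scans enter the table.

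- SAP 3.1.2: "All by-visit summarizations will be conducted using data from Cycle 1, Cycle 2, and/or the last cycle, as applicable".
- SAP 3.9 sets the data used for other assessments. Laboratory summaries use all core-study cycles and/or on-study follow-up. For three others, "For vital signs, ECOG performance status, and ECG, only data collected from the first two cycles and/or on-study follow-up assessments will be analyzed". ECHO/MUGA is not mentioned.

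ECG gets the same three-level display in SAP 3.9.5: "Shift of normality status (normal, abnormal with no clinical significance, abnormal with clinical significance) from baseline to each selected post-treatment assessment time point". Laboratory data get more. Besides a shift table, SAP 3.9.2 says that "for continuous hematology and chemistry parameters, descriptive statistics will be presented for the changes from baseline".

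The scans are scheduled in the Protocol 3.2 flowcharts. Protocol 5.2, exclusion 5d, uses ejection fraction as a number: a baseline value of 50% or less excludes the subject.

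**The concern.** Every subject is scheduled to receive an anthracycline. It is given with MEDI4736, for which Protocol 7.1.8 lists myocarditis as a rare, possibly immune-mediated event. The safety profile belongs to the Phase 1 primary objective and is a Phase 2 secondary objective.

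The ECHO/MUGA display has two gaps. First, the SAP does not settle which scans the shift table contains, and its only general rule on visits fits the scan schedule poorly. Second, a three-level category cannot show movement inside a category. If ejection fraction drifted down while scans were still called normal, the tables would not show it. What is at stake is the completeness of the cardiac safety description.

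**Working it through.** **Inputs**

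- On-treatment scans, Protocol 3.2: Cycles 4, 6 and 9 for all subjects except cohort 0a; Cycles 3, 6 and 9 for cohort 0a. Each subject also has one baseline scan and one at the first On Study Follow-up visit.
- By-visit rule, SAP 3.1.2: Cycle 1, Cycle 2 and/or last cycle.
- PLD 40 mg/m² on Day 1 of each of up to 12 cycles, Protocol 3.1.7.

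**Step 1: overlap of rule and schedule**

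- {4, 6, 9} ∩ {1, 2} is empty, and so is {3, 6, 9} ∩ {1, 2}: 0 of 3 on-treatment scans in both schedules.
- Cycle 12 is in neither set, so a subject whose last cycle is 12 adds none.
- The last-cycle clause helps only when the last cycle is itself a scan cycle.

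The table takes the rule literally and assumes that a subject reaching a scan cycle has that scan.

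| Last cycle | Scans done on treatment | Scans the rule admits |
|---|---|---|
| 1–3 | 0 | 0 |
| 4 | 1 | 1 |
| 5 | 1 | 0 |
| 6 | 2 | 1 |
| 7–8 | 2 | 0 |
| 9 | 3 | 1 |
| 10–12 | 3 | 0 |

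The documents give no distribution of last cycles, so the loss can only be bracketed. If every subject stopped in Cycle 4, 1 of 1 scans would be kept. If every subject completed Cycle 12, 0 of 3 would be kept. Counting each possible last cycle once (a counting device, not a forecast), scans done are 2×1 + 3×2 + 4×3 = 20 and scans kept are 3. In cohort 0a the first scan comes one cycle earlier, which gives 3×1 + 3×2 + 4×3 = 21 done and 3 kept.

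The rule does not name the follow-up scan either, and SAP 3.9 names follow-up only for other data. For a subject who stops before the first scan cycle, that is the only scheduled post-baseline core-study scan.

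**Step 2: exposure at the scans, if every PLD dose is given in full**

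- Cycle 4: 4 × 40 = 160 mg/m² (cohort 0a, Cycle 3: 3 × 40 = 120)
- Cycle 6: 6 × 40 = 240
- Cycle 9: 9 × 40 = 360
- Follow-up: at most 12 × 40 = 480

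The scans most exposed to omission are therefore those that follow exposure as it builds up.

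**Step 3: what the category can and cannot show**

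- A fall judged clinically significant is recorded as an AE (SAP 2.2.4) and, if treatment-emergent, is counted in the TEAE tables. It would usually also move the scan to the third category.
- A fall that moves a scan from normal to abnormal without clinical significance shows as a shift, provided that the scan is in the table.
- A fall within one category, not judged significant, shows in neither.

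For illustration, suppose a reader calls any value above 50% normal. A fall from 70% to 51%, 19 points, is then normal to normal unless someone judges the fall itself abnormal or significant. The documents do not say how status is assigned. The count of planned outputs is 1 shift table, 1 listing, and 0 tables or figures of ejection fraction, its change or a threshold fall. SAP 3.1.2 also gives a format for continuous variables, but no section or table names ejection fraction as one.

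**The case against.** The strongest reply is that little is left uncovered. Exclusion 5 removes subjects with clinically significant cardiovascular disease or a baseline ejection fraction of 50% or less, so few should start in the worst category. A later significant fall would then both shift and become an AE. That stands, and it limits the numeric part of this point to within-category falls that nobody judged significant.

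On visits, SAP 3.1.2 ends with *as applicable*, SAP 3.9.6 says *selected*, and SAP 3.9 itself uses laboratory data from all core cycles, so the rule is not an absolute cap. A reading that nearly empties a planned table is unlikely to be intended. That stands too. It is a reason to state the time points; it does not tell the programmer which ones to use.

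Numeric LVEF may not be collected on study. The documents do not say, and an eligibility cut-off does not prove that an eCRF field exists. The numeric part of the fix is therefore conditional. Gains will also be modest where 3+3 cohorts are shown separately. The protocol's version history notes that extra scanning above 550 mg/m² was dropped because the maximum here is 480.

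A reader might go further and infer that the plan breaks a protocol commitment, or treats ECHO/MUGA less well than ECG. Neither is supported: Protocol 4.2.2 names summaries of AEs, laboratory data and vital signs only, and ECG gets the same three-level shift.

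**Conclusion.** The point holds as a modest one. As written, the SAP does not define the ECHO/MUGA time points. Its general by-visit rule matches no scheduled on-treatment scan unless a subject's last cycle happens to be a scan cycle. Read literally, each subject contributes at most one on-treatment scan and a subject who completes treatment contributes none. Separately, within-category falls not judged clinically significant appear in no planned summary; at best they appear in the listing, if it carries the numeric value.

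A reader might infer that important falls in ejection fraction would go unreported, or that some share of them would be hidden. The documents do not support the first, because significant falls reach the AE tables. They do not allow the second to be calculated, because they give no normal limit, LVEF distribution or frequency of falls.

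The conclusion rests on the flowchart schedule and on a literal reading of SAP 3.1.2, which its own qualifier softens. It affects the cardiac safety description only. No hypothesis test or stopping rule depends on it.

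**What to change.** In SAP 3.9.6 and Table 14.4.8:

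1. State that the shift uses every scheduled ECHO/MUGA: Cycle 4 (Cycle 3 for cohort 0a), Cycles 6 and 9, and On Study Follow-up. Mark this as an exception to SAP 3.1.2.
2. Add a shift from baseline to the worst post-baseline category. Say whether treatment-extension scans (Protocol 8.9.1) count toward it.
3. Where the eCRF already holds numeric LVEF, add LVEF and its change from baseline at those scans, and the number and percentage of subjects whose worst post-baseline value is 50% or less, the protocol's own eligibility limit. Flag changes of modality, since the flowcharts allow either test. A count of falls of at least 10 points is optional; that threshold is a display proposal, not taken from the documents.

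If numeric LVEF is not captured, make only changes 1 and 2. Retrieving values from about 6 to 9 sites would no longer be cheap.

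The cost is SAP wording and one extra table panel from scans already scheduled, plus a modality check per subject where change 3 applies. The downside is small numbers at the later scans as subjects stop treatment.
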